13 ETHICAL AND REGULATORY CONSIDERATIONS	
14. DISSEMINATION POLICY	
15. REFERENCES	
16. APPENDICIES	

ii. LIST OF ABBREVIATIONS

BAP1 BRCA-associated protein 1

CA Competent Authority

CAG Confidentiality Advisory Group

CI Chief Investigator
CRF Case Report Form

FEV1 Forced expiratory volume in 1 second

FISH fluorescence in situ hybridisation

GCP Good Clinical Practice

GMP Good Manufacturing Practice

ICF Informed Consent Form

ICH International Conference on Harmonisation of technical

requirements for registration of pharmaceuticals for human

use.

IHC Immunohistochemical

ISF Investigator Site File (This forms part of the TMF)

ISRCTN International Standard Randomised Controlled Trials

Number

MDT Multi-Disciplinary Team

MTAP methylthioadenosine phosphorylase

NHS R&D National Health Service Research & Development

PI Principal Investigator

PIC Participant Identification Centre
PIS Participant Information Sheet

PET-CT Positron Emission Tomography CT

PPI Patient and Public Involvement

PM Pleural Mesothelioma
QA Quality Assurance
QC Quality Control

REC Research Ethics Committee
SDV Source Data Verification

SOP Standard Operating Procedure

SSI Site Specific Information

TMF Trial Master File

TMG Trial Management Group
TSC Trial Steering Committee

iii. TRIAL SUMMARY

Trial Title	Reducing Repeat Pleural Biopsies In Suspected Cancer – a study of the TARGET trial cohort			
Internal ref. no. (or short title)	REPLICA			
Trial Design	additional diagnostic tests in no could increase the diagnosis ramalignancy. Standard pathway	A UK based multicentre study to evaluate whether performing additional diagnostic tests in non-diagnostic pleural biopsies could increase the diagnosis rate in suspected pleural malignancy. Standard pathway vs proposed (involving additional diagnostic tests) pathway		
Trial Participants	A study of the 59 participants who enrolled in the RCT TARGET study at 8 UK sites between September 2015 and September 2018. Inclusion criteria included suspicious pleural thickening on CT scan, non-diagnostic pleural biopsy and MDT decision to perform further CT-guided biopsy to pursue a diagnosis.			
Planned Sample Size	59 participants were enrolled in TARGET. Total sample size is 118, as each participant provides matched data for both standard and proposed pathways. 129 biopsy samples available in total.			
Follow up duration	12 months (already completed as part of TARGET trial)			
Planned Trial Period	12-18 months total			
	Objectives	Outcome Measures		
Primary	Identify patients for whom additional pathological testing would have yielded a definitive diagnosis on baseline biopsy, avoiding the need for further invasive tests	Identification of malignancy on biopsy (binary; diagnostic vs non-diagnostic) via: i) histopathological confirmation on standard testing or histopathological features of PM with demonstrated BAP1, p16 or MTAP deletion or iii) Multi-disciplinary Team (MDT) diagnosis		
Secondary	i) Investigate whether additional pathological testing would have shortened the overall time to diagnosis and ii) Investigate whether additional testing would have reduced costs	i) Total number of biopsies required ii) Time to diagnosis iii) Stage at diagnosis iv) Number of MDT discussions required v) Biopsy-associated costs vi) Biopsy-related adverse events		

in whom additional testing would have provided a definitive diagnosis

iv. FUNDING AND SUPPORT IN KIND

FUNDER(S) (Names and contact details of ALL organisations providing funding and/or support in kind for this trial)	FINANCIAL AND NON FINANCIALSUPPORT GIVEN
Southmead Hospital Charity [name] [contact]	Research grant
NBT NHS Trust	Salaries for [name], [name], [name], [name]
NIHR	Salary for [name]
University of Bristol	Salary for [name]
University of West of England	Salary for [name]

v. ROLE OF TRIAL SPONSOR AND FUNDER

The Sponsor and Funders have no role or remit in the study design, conduct, data analysis and interpretation, manuscript writing or dissemination of results.

vi. ROLES AND RESPONSIBILITIES OF TRIAL MANAGEMENT COMMITEES/GROUPS & INDIVIDUALS

Study management group:

Responsible for oversight of the study. It will monitor trial progress, ensure all practical details of the trial are progressing well and feed back to the sponsor. The study management group will be chaired by the CI and will include all members of the named research team. It will meet 4 times during the study period.

Patient and Public Involvement group:

IRAS ID 329574

This will involve a specialist nurse and trial co-ordinator communicating details of the trial progress to a group of mesothelioma patients and carers as the study progresses.

Study delivery group:

This involves the people responsible for retrieving histological samples and performing and reporting the pathological tests. They will ensure accuracy and reproducibility of the tests, and updating the investigators on progress.

vii. Protocol contributors

Protocol authors: [name], [name], [name], [name], [name]

Study design has involved extensive PPI input. This has led to clarification of terms and gaining further PPI feedback which has resulted in patient-centred justification of study goals.

[figure not shown]
viii. KEY WORDS: Pleural malignancy, Pleural biopsy, mesothelioma, tumour

suppressor gene, multi-disciplinary team, diagnostic yield

ix. TRIAL FLOW CHARTS

[figure not shown]
TARGET trial flow chart from TARGET trial Protocol version 8, 23/3/18

REPLICA study flow chart:

1 BACKGROUND

Plain English Summary:

Pleural mesothelioma (PM) is a cancer that affects the outside lining of the lung, caused by asbestos exposure. The UK has the highest rate of PM in the world, but despite recent treatment advances, average life expectancy remains under a year from diagnosis. Prompt diagnosis is therefore vital.

People with suspected PM usually require a biopsy of the lung lining to confirm the diagnosis, guide treatment and assist with compensation claims. However, some people need multiple biopsies which increases the risk of biopsy-related complications and prolongs the diagnostic process, causing additional stress and anxiety.

Some people with mesothelioma can deteriorate rapidly. A prolonged time to diagnosis could mean the time window in which someone is sufficiently strong to tolerate life-prolonging treatment is missed.

We believe doing additional tests on initial biopsies will increase the chance of diagnosing PM, avoiding repeat biopsies. This will shorten the period of anxious uncertainty and allow patients to start anti-cancer treatment sooner, improving their chances of survival. Reducing the number of biopsies will eliminate the risks associated with multiple procedures and free up space for other patients with suspected cancer, improving their diagnostic pathway as well.

The extra tests – while not genetic tests – look for markers of genetic changes that happen in PM. Genes are the building blocks in every cell of our bodies that make up who we are and how our bodies behave. Some genes work to stop tumours appearing and, if they do appear, stop them growing. PM tumours can stop these protective genes working or make them disappear, which allows the tumour to grow and spread inside the body. The markers affected in PM are called BAP1, p16 and MTAP and we can test biopsy samples for these. If all three have disappeared, then we can make a diagnosis of mesothelioma.

We previously conducted a study of people with suspected PM who required further biopsies as their first biopsy did not diagnose the condition. All patients consented to be in this trial and an application is underway for approval to perform additional tests on the trial samples. We want to re-test their original and follow-up biopsy samples for BAP1, p16 and MTAP to see whether this would have made the diagnosis sooner and removed the need for further biopsies. We will investigate how many biopsies could have been avoided, how much time would have been saved, and what cost-savings this would have offered the NHS.

BAP1, p16 and MTAP are not routinely used in clinical practice and are not available at many hospitals, despite being relatively inexpensive. BAP1 is already available in NBT and MTAP is undergoing set up. The cost of setting up MTAP is between £150-£400.

We hope our research will show how useful these tests are and how much benefit they offer to patients and NHS services, so they can be used more widely in routine care. Ultimately, we expect our research to be included in national guidelines and change clinical practice across the UK and worldwide.

Scientific summary:

Pleural Mesothelioma (PM) is a primary incurable malignancy of the pleural surface, associated with prior asbestos exposure. Median survival is 9-12 months. Chemotherapy offers marginal therapeutic benefit, but combination immunotherapy has shown promise in recent phase III trials. [1, 2]

Diagnosing PM can be challenging. Radiology supports diagnosis but pathological diagnosis is the gold standard. Some patients present with pleural effusions but pleural fluid sensitivity for PM is low. Pleural biopsy has higher diagnostic sensitivity, but this drops with smaller samples and certain histological subtypes [3]. As a result, some patients undergo multiple investigations, with increased risk of complications and delays to treatment initiation.

Our research unit has previously studied potential approaches to enhance the PM diagnostic process. The multi-centre randomised TARGET trial studied whether Positron Emission Tomography CT (PET-CT) directed biopsy improved the diagnostic yield of biopsies in people with previous non-diagnostic biopsies [4]. PET-CT did not improve diagnostic rates and some repeat biopsies were also non-diagnostic, necessitating further invasive procedures.

Recent advances since TARGET have broadened the panel of tests available for PM biopsy samples. Homozygous deletion of the 9p21 locus is one of the most common genetic alterations in PM, affecting a cluster of tumour suppression genes that show diagnostic promise. These are BRCA-associated protein 1 (BAP1), p16 and methylthioadenosine phosphorylase (MTAP) [4, 5].

BAP1 is a tumour suppressor gene that is mutated in 40-60% of PM tumours, causing loss of BAP1 expression. A 2017 meta-analysis showed BAP1 loss had moderate diagnostic sensitivity (area under the curve of 0.72) with 100% specificity, making it an excellent 'rule-in' test for PM [6].

P16 deletion occurs in 80% of PM and is demonstrated using fluorescence in situ hybridisation (FISH). Diagnostic sensitivity of P16 FISH is 0.53, but 0.76 if combined with BAP1 testing [7].

FISH is not performed in all laboratories but immunohistochemical (IHC) staining is universally available. IHC expression of the protein product of the MTAP gene has been shown to be an accurate and reproducible surrogate marker for p16 FISH, with 78% sensitivity and 96% specificity for homozygous p16 deletion and is faster and cheaper to run [8]. When used in combination with BAP1, MTAP IHC has 100% specificity and 76.5% sensitivity for differentiating between malignant and benign mesothelial disease [6].

BAP1, p16 FISH and MTAP are used in some UK centres but are not universally available nor routinely recommended in current guidelines [9-11].

2 RATIONALE

This study aims to evaluate the diagnostic benefit of BAP1, p16 FISH and MTAP in suspected PM by re-testing the initial non-diagnostic/negative biopsy samples from TARGET trial participants to evaluate whether the additional tests would have yielded a definitive diagnosis sooner. If we demonstrate that running these inexpensive tests leads to earlier diagnoses and reduces the need for repeat biopsies, wider adoption of this test panel into routine clinical practice will follow. Our research will inform subsequent national guidelines, leading to changes in mesothelioma MDTs across the country. This will benefit patients (through shortened diagnostic pathways) and the NHS (through cost-savings and increased availability of biopsy appointments).

PPI representatives were universally supportive of the study, citing the potential benefits to them of fewer biopsies, reduced waiting time for a diagnosis, reducing stress and worry from non-diagnostic biopsies and reduced anxiety from all these factors.

2.1 Assessment and management of risk

- Patients: no patients are being recruited as part of this study (we are using historic data and stored samples from a previous study where patients consented to their anonymous information being used for future research).
- Data: risk of missing data: there is a risk that some biopsy samples will be insufficient in size to undergo the stains required. In another study that required pulling of much older biopsies, less than 10% of samples were missing.

3 OBJECTIVES AND OUTCOME MEASURES/ENDPOINTS

This research aims to answer the question: Could testing for BAP1, P16 FISH and MTAP IHC have removed the need for further invasive procedures in patients with suspected PM and an initial non-diagnostic biopsy?

We will address this question via the following objectives:

- Identify participants from the TARGET trial population (n=59)
- Extract historic biopsies (initial and repeat) from NHS pathology laboratories (n=129)
- Perform BAP1 and MTAP on all extracted biopsies. Where this fails to yield a diagnosis, perform additional p16 FISH.
- Identify patients for whom additional testing would have yielded a diagnosis, avoiding the need for further invasive tests (primary outcome).
- Investigate whether additional testing would have shortened the overall time to PM diagnosis (secondary outcome).
- Identify TARGET participants who ultimately received a clinico-radiological diagnosis, i.e. no tissue diagnosis was made, in whom additional testing would have provided a definitive diagnosis (sub-group analysis).

Primary and secondary outcomes, and outcome measures can be found in the study summary table.

4 TRIAL DESIGN

Observational study using historic data and stored samples from a multi-centre randomised controlled trial (TARGET, ISRCTN 14024829), where each participant will act as a case (additional tests applied to stored samples) and an internal control (initial outcomes using standard testing only).

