5 TRIAL SETTING

Historic data and stored samples from patients that consented to participate in the multicentre TARGET trial will be retrieved from NHS pathology laboratories and analysed at NBT.

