7.4 Storage and analysis of clinical samples

Histological samples from TARGET patients are NHS clinical samples and as such are stored in NHS pathology laboratories. They will be retrieved for staining and analysis at NBT laboratories and may be transferred off North Bristol NHS Trust premises to facilitate the undertaking of p16 FISH. A Material Transfer Agreement will be completed for any and all transfers of samples to and from external sites for storage and/or analysis. Following completion of sample analysis they will be returned to the relevant NHS pathology laboratories.

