7.5 End of trial

The trial will be completed when all samples have been stained and reported, with all pathology reporting queries answered.

8 Safety reporting

There is no new patient contact, intervention or sampling as part of REPLICA. There is therefore no safety reporting required.

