10 STATISTICS AND DATA ANALYSIS

The independent variable is the availability of BAP1, p16 FISH and MTAP testing (binary; available *vs* not available). The primary outcome is identification of malignancy on biopsy (binary; diagnostic *vs* non-diagnostic), with diagnosis defined as i) histopathological confirmation on standard testing or ii) histopathological features of PM with demonstrated BAP1, p16 or MTAP deletion or iii) Multi-disciplinary Team (MDT) diagnosis. It is assumed that confirmation of a malignant diagnosis stops the diagnostic pathway with no additional biopsies required. Any subsequent biopsies for these participants will not be included in the analysis, preventing double-counting. Secondary outcomes include total number of biopsies required, time to diagnosis, stage at diagnosis, number of MDT discussions, biopsy-associated costs, biopsy-related adverse events and survival. Potential confounding variables include age, sex, biopsy method and tumour histology and these will be adjusted for, when possible, in the analysis.

Outcome measures will be tabulated for standard and proposed pathways and compared using descriptive statistics (including the McNemar test). Univariable and multivariable logistic regression will look for an association between the availability of these tests and likelihood of a diagnostic biopsy. The relationship between secondary outcomes and availability of the tests will be evaluated using adjusted and unadjusted regression analyses and time to event analysis (cox proportional hazard model).

Sample Size:

Total number of patients: 59

Total histological samples for analysis: 129 (all participants had multiple biopsies)

REPLICA

IRAS ID 329574

Each participant will be assessed as a case (proposed pathway) and as an internal control (standard pathway) generating two groups of 59 = 118 records for inclusion in the study

Sample size is determined by the number recruited to the TARGET study which demonstrated diagnostic sensitivity (without these additional tests) of 30%. A sample size of 118 (59 in each arm) will allow detection of an increased diagnostic rate of 60% with 95% confidence intervals of +/- 8.8% (based on BAP1 loss prevalence of 60%).

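### The protocol does not hold the morphology read constant between the historical control and the new NBT result, so a re-read effect could be credited to the markers

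*Protocol*

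**What the plan says.** Section 4 (Trial Design) builds two records per participant. In one, "each participant will act as a case (additional tests applied to stored samples"); in the other the same person is an "internal control (initial outcomes using standard testing only").

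The control results are historical. According to the Trial Summary, participants enrolled in the "RCT TARGET study at 8 UK sites between September 2015 and September 2018". Section 6 shows that all had a non-diagnostic pleural biopsy at entry.

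The case results are new. Section 5 says samples "will be retrieved from NHS pathology laboratories and analysed at NBT". Section 7.4 adds: "They will be retrieved for staining and analysis at NBT laboratories and may be transferred off North Bristol NHS Trust premises", the transfer being for p16 FISH. Section 7.5 reads: "The trial will be completed when all samples have been stained and reported, with all pathology reporting queries answered".

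Section 10 attributes the contrast to one factor: "The independent variable is the availability of BAP1, p16 FISH and MTAP testing". A biopsy counts as diagnostic by (i) confirmation on standard testing, (ii) PM morphology together with loss of BAP1, p16 or MTAP, or (iii) an MDT diagnosis. The potential confounders named are age, sex, biopsy method and tumour histology. Reader, laboratory and period are not among them.

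**The concern.** Criterion ii has two parts, a morphology judgement and a marker result. Only the second is what the study sets out to evaluate. To isolate it, the morphology judgement must be the same in both records of a participant. The protocol neither says that the original read is carried forward nor asks for a new standard-stain read to serve as the control.

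Section 3 also calls for p16 FISH where BAP1 and MTAP have not settled the diagnosis. Somebody must therefore decide within REPLICA, biopsy by biopsy, whether a diagnosis has been reached. That makes a fresh morphology judgement plausible, although it is not written down.

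If one is made, a biopsy can become diagnostic partly because a different pathologist, years later, sees PM features that the original report did not record. The whole conversion would still be attributed to the markers. The study hopes to inform national guidelines on this test panel, so the attribution matters. Every control record is historical and every case record is new, so reader, laboratory and period are fully aliased with pathway. No regression term can recover the marker effect if the standard-stain verdict was not recorded when the slide was read.

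**Working it through.** **The two records side by side**

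| Element | Control record | Case record |
|---|---|---|
| Source | Original TARGET-period outcome | Stored tissue, newly stained and reported |
| Laboratory | NHS laboratories of 8 sites | NBT, p16 FISH possibly elsewhere |
| Markers | No | Yes |
| Morphology judgement | Original report | Not stated: original report or new NBT read |
| Criteria i and iii | Original result | Not stated whether carried over or re-applied |

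The markers row is the intended contrast. The last two rows are left open.

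**Figures in the protocol.** Section 10 gives precision figures only. With n = 118 and half-width 1.96 × √(p(1−p)/n), they come to 8.84, 8.27 and 7.22 points for 60%, 70% and 80%, against the stated 8.8, 8.2 and 7.2. They reproduce (8.27 looks truncated) but do not bear on this point. There is no figure for how often a re-read upgrades a biopsy.

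**Possible size under an assumed upgrade rate r of 5-15%**

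Inputs: 59 participants (section 10); BAP1 loss in 40-60% of PM and a BAP1 plus MTAP sensitivity of 76.5% (section 1); r assumed.

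- Upgrades of morphology: 59 × 0.05 = 2.95, about 3; 59 × 0.15 = 8.85, about 9.
- Under criterion ii an upgrade counts only with marker loss. Taking 40% as the low share and 76.5% as the high one: 2.95 × 0.40 = 1.2, about 1; 8.85 × 0.765 = 6.8, about 7.
- As points of yield: 0.05 × 0.40 = 2.0 points; 0.15 × 0.765 = 11.5 points. Section 10 plans for a rise from 30% to 60%, that is 30 points.
- If criterion i or iii is re-applied at NBT, an upgrade can count without marker loss, and the range is the full 3-9 of 59 (5-15 points).

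The scaling assumes that upgraded biopsies are PM and show marker loss at the rates cited. p16 FISH could raise the share somewhat above 76.5%, but the count cannot exceed the 9 upgrades.

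**Sensitivity of the paired test.** On the initial biopsy every control is non-diagnostic, so discordant pairs can run only one way. With b such pairs the exact two-sided McNemar p-value is 2 × 0.5^b. For b = 5 it is 0.0625; for b = 6 (6/59 = 10.2%) it is 0.031. At a two-sided 0.05 level, which the protocol does not state and is assumed here, six conversions suffice. If re-read conversions alone could count, the chance of six or more in 59 would be 7.4% at r = 5%, 54.6% at 10% and 89.4% at 15%. That applies only where criterion i or iii is re-applied.

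**The case against.** A reader might infer that a second pathology review is planned, that the contrast therefore certainly mixes two effects, and that 3-9 participants will be wrongly credited. The documents do not support this.

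- No re-review of standard stains is written anywhere. Section 4 describes the case only as added tests, and the study delivery group's task is to perform and report those tests. Section 7.3 extracts the original biopsy results and histological diagnosis. A fair reading is that the original read serves both pathways, in which case the problem largely disappears.
- Section 10 does not claim that the two records differ in nothing but test availability. It names availability as the independent variable and lists potential confounders.
- Under criterion ii a re-read without marker loss cannot make a biopsy diagnostic. The full 3-9 needs every upgrade to count, which requires criterion i or iii to be re-applied at NBT. No section says that it will be.
- A fresh read may also fail to find PM features and so exclude a biopsy with marker loss. Compared with carrying the original read forward, the yield could fall as well as rise.
- The historical pathway is the natural comparator for the question in section 3, and reading order could be set out in an SAP.

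These points limit the finding to a conditional one and reduce its size. What stands is that criterion ii needs a morphology judgement and that nothing in the design keeps it the same in both records. An SAP could resolve this by carrying the original read forward. It could not do so by adjustment after the slides have been read.

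**Conclusion.** The concern holds in conditional form. The control is a historical multi-site outcome, the case is produced anew at NBT, and the morphology part of criterion ii is not held constant between them. If NBT makes that judgement afresh, the yield attributed to test availability may be overstated, and the data would not show by how much.

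The size rests on an assumed upgrade rate, not on a figure in the protocol: about 1-7 of 59 participants under criterion ii, with 3-9 as the range only if criterion i or iii is re-applied. Against the planned 30-point gain, 2.0-11.5 points would not by itself account for a result of the size hoped for, but the upper end would distort the estimate materially. The change should be made before any slide is read.

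**What to change.** Choose one of two routes and state it in sections 4 and 10.

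1. **Carry the original read forward.** State that the morphology read and the criterion i result from original standard testing apply in both pathways, so that only the marker results are new. This costs a sentence. It works only if the original reports say clearly enough whether PM features were present.
2. **Record a standard-stain verdict first.** The NBT pathologist who judges criterion ii records, for each biopsy, whether the standard stains are diagnostic, show features of PM, or show none. This is done before marker results are released and without knowledge of the final diagnosis. Count as the marker effect only participants who are non-diagnostic at that read and become diagnostic once the markers are added. Report re-read upgrades separately.

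The second route costs one extra recorded field per biopsy (129 at most) and access to the standard-stained sections, which section 7.4 does not explicitly cover. It needs no reader beyond the one judging criterion ii. The yield attributed to the markers may come out lower.
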